13.3 Sponsor's obligations

The Safety Desk will document each SAE, check it and query additionally required information.

Fulfilling sponsor's responsibilities, the Investigator will review each SAE again for seriousness and relatedness. Furthermore he will assess whether a serious adverse reaction is expected or unexpected (SUSAR) according to the current version of the IMPD, and whether any SAE might influence the benefit-risk-ratio or might require changes in the conduct of the trial.

It is the duty of the sponsor's Safety Desk to inform the Ethics Committee, the Competent Authority and participating investigators of all SUSARs in accordance with legal requirements (immediately, fatal or life-threatening SUSARs by the latest within 7 calender days, other SUSARs by the latest within 15 calender days of first knowledge. For fatal or life-threatening SUSARs, additional information will be provided as relevant within a further 8 days.). SUSAR follow-up reports will be submitted, if appropriate.

The Safety Desk will observe SUSAR cross reporting obligations with other trials of the same sponsor investigating the same active substance, if any.

The Investigator is responsible for the ongoing safety evaluation of the trial. The Safety Desk and the Investigator will inform each other immediately about any relevant safety information coming to their knowledge. In case of safety relevant issues (besides SUSARs) which require expedited reporting, the Safety Desk will support the Investigator in submitting an appropriate report in due time. This includes issues which might materially alter the current benefit-risk assessment of an investigational medicinal product or that would be sufficient to consider changes in the investigational medicinal product's administration or in the overall conduct of the trial as well as urgent safety measures to protect the subjects against any immediate hazard.

Annual safety reports will be prepared and submitted in accordance with legal requirements (Development Safety Update Report, DSUR). The Investigator is responsible for providing the updated benefit-risk assessment of the trial for the report (passages requiring medical assessment). The Safety Desk is responsible for preparing the other parts of the report, finalizing it and submitting it to the Competent Authority and the Ethics Committee in due time. The report will be prepared annually from the date of the initial clinical trial authorisation and submitted within 60 days of data lock point (day before anniversary of initial authorisation). Additional reports will be prepared on request by the Competent Authority or the Ethics Committee.

Details of all AEs will be reported to the Competent Authority on request.

14. Anticipated Risks for the Subjects

According to the first-in-man experience doses of tTF-NGR up to 4 mg/m² are tolerated without side effects when infused over a central venous access for 1 hour with weekly intervals. Single patients have been treated up to 5 times with weekly intervals. Anticipated side effects and toxicities are classified as those related to infusional reactions, venous thrombosis, arterial vascular occlusion and embolism, disseminated intravascular coagulation (DIC), tumor bleeding, antibody formation, liver toxicity, and a transient thrombocytopenia. A detailed justification of the starting dose for tTF-NGR in this trial is given in the IMPD.

14.1 Infusional reactions

Allergic reactions including rash, fever, rigors and bronchospasm are possible after infusion of proteins. This did not happen during the treatment of the first patients. However, in case these side effects occur, patients will be premedicated with chlorpheniramine, paracetamol and corticosteroids to prevent such reactions.

14.2 Venous thrombosis

The occurrence of venous thrombosis has not been observed in the patients treated with tTF-NGR. Additionally, such an event is unlikely, since there are rare binding sites for the NGR-binding moiety in venous endothelial cells of adult vessels. However, after repeated injections of the IMP into the tail veins of mice, acral necrosis occurred and high local concentrations might theoretically induce venous thrombosis. Thus, tTF-tTF-NGR Phase I Study, Study Protocol, Version 10, 28.07.2016

NGR has to be infused over a time period of 1 hour via a central venous access. Patients have to be treated in-house with all appropriate drugs for fibrinolysis and anticoagulation ready to use.

14.3 Arterial vascular occlusion and embolism

The occurrence of arterial vascular occlusion and/embolism has not been observed in the patients treated with tTF-NGR. It also did not occur in mice treated within the therapeutic dose range. However, in the safety pharmacology studies with mice to establish limiting toxicity and maximum tolerated dose, we have observed pulmonary embolism and indirect signs of infarction in brain histology of mice deceasing upon treatment (see IMPD). Thus, patients have to be treated in-house with close back-up of an intensive care unit (ICU), their vital parameters (including ECG-monitoring, capillary O₂-saturation) and clinical symptoms have to be checked upon continuously during the infusion and for at least 5 hours afterwards by the investigator or a trained physician and in intervals later as specified by the protocol. Repeated checks on appropriate blood and serum parameters such as troponin and creatinine phosphokinase isoenzymes are outlined above. Appropriate drugs, including those for fibrinolysis and anticoagulation have to be ready for use.

14.4 DIC

DIC was not observed in the patients treated with tTF-NGR thus far. However, DIC can occur theoretically upon dose escalation. Thus patients have to be treated in-house as outlined above and have to be tested repeatedly for blood and serum parameters such as platelet count, D-dimer, fibrinogen, fibrin split products, plasmatic coagulation parameters as outlined above.

14.5 Tumor bleeding

During the preclinical studies we have observed thrombosed tumor vessels with blood pooling, disruption of vessels and intratumoral bleeding (see IMPD). This effect is part of the mechanism of action of tTF-NGR, which enriches and binds in tumor vessels and causes local thrombosis. During all animal studies we have observed sporadic deaths of treated mice with no clear dose-dependency. However, we had the impression this was occurring more often with animals carrying large tumors of >0.5 cm³. Thus, tumor bleeding may occur. It may preferentially occur in patients with tTF-NGR Phase I Study, Study Protocol, Version 10, 28.07.2016 33 large tumor masses. Thus, patients have to be treated in-house with appropriate transfusions of platelets and red blood cells available and prepared for.

14.6 Antibody formation

Human anti-human antibody (HAHA) formation is a theoretical concern although highly unlikely. 1. The amino acid sequence of the tTF-moiety is the unchanged human sequence and thus should be of low or absent immunogenicity. 2. The short NGR-binding moiety used has been reported as being of very low or absent immunogenicity (Di Matteo P et al. Immunogenic and structural properties of the Asn-Gly-Arg (NGR) tumor neovasculature-homing motif. Mol. Immunol. 43: 1508-1518, 2006). 3. The Histag consists of less than 50 amino acids. However, antibody formation could occur after repeated application and possibly interfere with the therapeutic activity of tTF-NGR. Thus, patients with longer treatment duration will be monitored for HAHA formation.

14.7 Pregnancy, Breast Feeding and Fathering of a Child

There are no data on embryonal or fetal toxicity of tTF-NGR. Since endothelial cells in blood vessels of a growing fetus might express the targets CD13 and □lpha_v□eta₃, treatment of pregnant women has to be avoided. Premenopausal women are only allowed to participate in trials with the IMP under strict birth control and upon a negative result of a pregnancy test. Female patients are considered to have no child bearing potential if they are permanently sterile or post-menopausal. Permanent sterilization methods include hysterectomy, bilateral salpingectomy and bilateral oophorectomy. A postmenopausal state is defined as no menses for 12 months without alternative medical cause.

Female patients of childbearing potential (and male patients with a partner of child bearing potential) must agree to use a highly effective contraceptive method (Pearl index <1) throughout the study period and during the 2 months thereafter.

14.8 Liver toxicity

Since we have observed increase in bilirubin levels to values higher than the upper limit normal in the dog toxicology (see IMPD) liver toxicity including bilirubin values has to be monitored carefully throughout the study.

14.9 Transient thrombocytopenia

We have observed transient platelet drops under therapy with tTF-NGR in single patients before, which are possibly due to consumption of platelets within the tumor vascular infarction. Thus, this phenomenon might belong to the mechanism of action of the IMP. It is therefore necessary to treat the patients within this phase I study as "in-house" patients, to make fast transfusions of platelets realistic.

15. Assessment of disease status

Assessment of disease status is made at the time points given in the study calendars. Disease response criteria are according to the RECIST guidelines. The study radiologist will give special attention to tumor necrosis in lesions not shrinking in their outer diamenter and report these in addition. As a surrogate parameter for target hit, MRI will be performed. Vascular volume fraction will be measured to quantify reduction of blood flow in the tumor induced by tTF-NGR. These data will be reported in addition.

[figure not shown]
16. Statistical Considerations

All statistical evaluations within the study will be performed by [name]. [name].

16.1. Estimation of the number of patients needed to complete this trial.

The number of patients needed for completion of this trial is determined by the occurrence of dose limiting toxicity (DLT).

A first patient will be treated daily with tTF-NGR by 1-hour iv infusions for 5 days. Starting dose will be 1 mg/m²/day, intraindividual dose-escalation will be performed in 0.5 mg/m²/day steps upon a rest period of 16 days for the next treatment cycle of 5 days in this patient. If diagnosed with progressive disease (PD) after 2 cycles or clinically as judged by the investigator even before, this patient will go off study and will be replaced by a further patient in whom individual dose escalation will be resumed. Upon occurrence of DLT up to 5 further patients will be treated at this specific dose in a verification cohort. Further procedure such as de-escalation and definition of MTD and dose level recommended for further clinical trials will be performed as described above. Thus, a minimum number of patients to reach objectives of this study are envisaged as being 7 patients. This number of patients represent 1 patient for first dose-escalation with DLT at the highest dose, starting the verification cohort and reproduction of DLT in the first patient (of up to 5 patients) of the verification cohort, de-escalation with -0.5 mg/m 2 /day in 5 further patients with \leq 1 additional DLT.

Possible higher numbers of patients in situations such as with no additional DLT in the verification group and further dose-escalation is possible, but cannot be determined before the study with confidence.

17. Study duration, Premature Termination of the Study

Planned start date of the study (FPFV, first patient first visit): 01.11.2016

Planned end date of recruitment (LPFV, last patient first visit): 01.11.2017

Planned end date of the study: 01.05.2018

Planned duration of single patient participation: according to occurrence of DLT and antitumor activity

Planned duration of recruitment: 01.11.2016 - 01.11.2017

Planned overall duration of the study: 01.11.2016 - 01.05.2018

Planned duration of follow up of individual patients within study: 3 months

Definition of the End of the Study

To allow reasonable time for evaluation and report, the end of study is plannned to be at "last patient last visit" (LPLV).

Premature Study Termination

Premature Termination of Study Participation of a Single Patient

A patient is free to withdraw consent and discontinue participation in the study at any time, without prejudice to further treatment according to standard clinical practice. In this case the patient will be asked to permit the conduct of the study termination visit. In certain circumstances the investigator may exclude a patient from further study participation irrespective of the patient's will. Reasons may be:

- treatment failure
- insufficient compliance
- further participation might jeopardize the patient's health or well-being
- the patient was administered medication which is not permitted
- termination of the entire study.

If, after treatment initiation, a patient's participation is realized not to agree with the inclusion and exclusion criteria, the Investigator will decide on further participation.

In case of premature termination, the reason will be recorded on the CRF.

Premature Termination of the Entire Study

The sponsor may terminate the entire study for relevant medical or administrative reasons. Reasons for termination will be documented in detail. Particular reasons for termination of the study may be:

- insufficient recruitment
- serious problems with the quality of the study data which cannot be solved
- discovery of an unexpected, serious and unacceptable risk to patients enrolled in the study
- new scientific evidence suggesting that study continuation is not justified.

18. Informed Consent

As the study is performed in Muenster, Germany and is a monocentric study, the informed consent form will be provided in German as in Appendix 2.

Prior to inclusion into the study, the investigator informs each patient about nature, significance, implications, and risks of the study as well as about the patient's right to withdraw from study participation at any time without any resulting detriment. Further, tTF-NGR Phase I Study, Study Protocol, Version 10, 28.07.2016

the patients are informed that an insurance has been taken out to cover risks originating from the study. According to the insurance conditions, they are advised to immediately inform the investigator if they were treated for an emergency and not to undergo any other medical treatment without prior consultation with the investigator.

Additionally, patients are handed out the patient information sheet incl. the informed consent form which are provided for this study. Patient consent in study participation must be given in writing. Before informed consent is requested, patients are left sufficient time for consideration. They are provided the opportunity for clarification of any study issues.

According to German drug law ("Arzneimittelgesetz") §40(2a) patients are informed that their disease related data are stored in a pseudonymized way and used for scientific evaluations. For study participation they must agree therein in writing.

The informed consent form is dated and signed by the patient and by the investigator. The originally signed informed consent form is archived in the investigator site file. A copy of the signed informed consent form (or a second original) is handed over to the patient together with a copy of the patient information sheet and a copy of the general conditions of the patient insurance.

If the patient is unable to write, in exceptional cases, instead of the written consent required, oral consent in the presence of at least one witness, who was also included when the patient was being informed may be given. The witness may not be anyone working at the study site nor a member of the investigating team. The orally given consent has to be documented in writing, dated and signed by the witness.

In case of any study issue which requires a change of the patient information sheet, patients already included into the study must, if relevant to them, be informed about these issues orally and in writing and their written consent in further study participation must be obtained.

Note: Before undergoing any study specific procedure the patient must have provided written informed consent!

19. Study Administration

This study will be conducted in compliance with the protocol, the International Conference on Harmonisation of Good Clinical Practice (ICH GCP) guidelines and the Declaration of Helsinki (Fortaleza, 2013), the requirements of the current German drug law ("Arzneimittelgesetz"), the current legal provisions regarding data protection, and the principals of Good Clinical Practice.

The present study will not be started before the competent ethics committee has given a favorable opinion and an approval by the competent federal authority has been obtained.

In case of substantial amendments, a new application will be submitted to the ethics committee and/or the competent federal authority. Changes will not be implemented unless the competent ethics committee has given a favorable opinion and/or the competent authority has granted an approval.

Issues, which always require a favorable opinion of the ethics committee are for example:

- inclusion of additional study sites,
- change of the investigator or his deputy,
- changes in any documents addressed to study participants or in any study information addressed to potential study participants.

According to German drug law §67, the investigator is required to notify the local surveillance authority about the beginning, the end and a premature termination of the study, about any substantial amendments and if the study is on hold. These notifications will be performed by an appointee of the sponsor (GCP-V, §12(3)).

Additionally, the investigator is required to notify the competent federal authority of the beginning of the study.

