Patients will be treated with tTF-NGR by 1-hour iv infusions via central venous access daily for 5 days every 3 weeks. Starting dose will be 1 mg/m²/day. Intraindividual dose escalation will be performed within one single patient in 0.5 mg/m²/day steps upon good toleration of the previous cycle. Patients within the dose-escalation part will be treated in sequence and not in parallel. Individual patients can undergo a maximum of 8 dose-escalations. The maximum number of 8 dose escalations is reached only if stable disease (SD) is ongoing upon 8 cycles of therapy. Dose-escalation is stopped before the maximum number of 8 escalation steps if tumor response, tumor progression or a Dose-Limiting Toxicity (DLT) is observed. In the case of SD and with good tolerability these patients can obtain further cycles without dose-escalation until tumor progression or Dose-Limiting Toxicity (DLT) and the next patient can start with dose-escalation cycles on the highest tolerable dose for the previous patient. A patient will undergo no further treatment if any of the criteria under 7.4 is reached.

Treatment will be followed by MRI tumor perfusion studies at cycles as decided by the Investigator as a surrogate marker for target-hit. MRI tumor perfusion studies will be performed before treatment onset, on day 1 (4-6 hours after application), and on day 5. MRI will be done not in every cycle of every patient, but in every patient of the verification cohorts in at least one cycle.

Toxicity monitoring will be performed according to the most recent version of the CTC criteria.

MTD is the dose below the dose leading to reproducible episodes of Dose Limiting Toxicity (DLT). DLT will be characterized by clinical, blood and serum monitoring at specified time points before and during study period.

Antitumor activity and response will be determined according to RECIST criteria with extent of disease evaluation before and after treatment period and in 3-monthly intervals thereafter, or as defined by clinical needs. Waterfall-analysis for response quantification in % of the marker lesions before treatment onset and at best response will be done centrally by the study radiologist.

Pharmacokinetic monitoring will be done as outlined below.

6. Eligibility criteria and patient registration

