6.1 Inclusion Criteria

Inclusion criteria for entry on trial are

- \triangleright age \geq 18 years
- histologically proven or cytologically confirmed solid malignant tumor or malignant lymphoma
- recurrent or refractory disease after standard therapy and with no known curative or survival-prolonging treatment options according to the judgement of the investigators
- > life expectancy of at least 6 weeks according to the judgement of the investigators
- Karnofsky performance status ≥ 50
- measurable disease with at least one marker-lesion measurable in 2 dimensions by Vascular Volume-Fraction-MRI
- adequate bone marrow function with absolute neutrophil count 1000/microliter and platelet count > 50/nl.
- normal global coagulation parameters (Quick, PTT, TZ, fibrinogen), no prophylactic anticoagulation
- ➤ adequate liver function (total bilirubin < 3x the upper normal limit (ULN), SGPT/SGOT < 3x ULN)

- adequate renal function (serum creatinine < 3x ULN)

- > no history of coronary heart disease, stroke, transitory ischemic attacks, pulmonary embolism, or deep vein thrombosis
- \succ time elapsed from previous therapy (including other IMPs) \geq 3 weeks with recovery from side effects

>

- exclusion of central nervous system (CNS) disease and CNS vascular abnormalities by MRI
- ability to understand and provide written informed consent
- written informed consent given
- ➤ for female patients with child-bearing potential exclusion of pregnancy by adequate testing within 48 hours prior to entry on study
- females of childbearing potential as well as fertile males must agree to use a highly effective form of contraception (Pearl Index < 1) during the study and for 120 days following the last dose of the IMP

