6.2 Exclusion criteria

- clinically significant unrelated illness which in the judgement of the investigators could compromise the patient's ability to tolerate the IMP or be likely to interfere with the study procedures or results
- known hypersensitivity reactions to prior application of E. coli-derived material
- women with breast-feeding activity
- concomitant use of any other investigational agent (agent for which there is currently no approved indication from regulatory authorities)
- > clinical application of any other drug with known antitumor activity
- prophylactic anticoagulation within the last 3 days

NOTE: Since this is a phase I study for end-stage cancer patients, patients who would be excluded from the protocol strictly for laboratory abnormalities only can be included at the Investigator's discretion. This will be documented as an exception to the criteria and will be signed and filed in the CRF and the Trial Master File.

Patient's eligibility for entry to the study will be assessed by the Investigator or their delegated representative physician. Distribution of **gender** in the study population will be random and gender will be no factor influencing accrual. tTF-NGR is not expected to differ in its effects in male and female patients.

Patients identified as eligible for entry into the study will be **registered** centrally through the study bureau of the Department of Medicine A (Hematology, Hemostaseology and Oncology) of the UKM.

tTF-NGR Phase I Study, Study Protocol, Version 10, 28.07.2016

7. Treatment Plan

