7.3. Other anti-cancer medication

Administration of any other anti-cancer medication including chemotherapy and biologic therapy and other IMPs is not permitted during study period. Palliative radiotherapy of single tumor-lesions e.g. causing tumor-related pain is allowed, however, these lesions have to be excluded from response judgement.

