Start 1 pt at 1 mg/m²/day with individual dose escalation at 0.5 mg/m²/day for 5 days every 3 weeks until any DLT (= dose "d1") or to a max of 8 cycles

Verification group (VG) of ≤5 further pts at d1 without indiv. dose esc.

(Verification group (VG) of ≤5 further pts at d1-0.5mg/m²/day without indiv. dose esc. in case a death occurs as DLT)

No further DLT in VG > resume dose escalation: start 1 pt of VG at d1 + 0.5 mg/m²/day (d), then as above

1 further DLT in VG > dose de-escalation d1 - 0.5 mg/m²/d, 5 further pts (d-1(-2))

>1 further DLT: d-1 = MTD

>1 further DLT > dose de-escalation, continue as above
```

Again, if a patient has been taken off the study due to a DLT or progressive disease, the patient may further be treated as follows. If the patient has stable disease or response and the DLT has been resolved, outside the study the patient may be treated

with the study medication on the highest tolerable dose level without DLT (§ 34 Declaration of Helsinki, Fortaleza 2013). In case of progressive disease or if the DLT has not been resolved, different treatment options are offered.

11. Study objectives and end-points

Primary Objectives

To evaluate the maximum tolerated dose (MTD) and the dose-limiting toxicity (DLT) of intravenously (i.v.) infused daily applications of tTF-NGR in patients with cancer (solid tumors and lymphomas), who had obtained all standard treatment known for their disease entity prior to entry on study.

Secondary Objectives

- 1. To determine the perfusion and vascular volume fraction of measurable tumor lesions versus normal reference tissue before and after tTF-NGR application by MRI as a imaging surrogate parameter for biological activity of the IMP.
- 2. To obtain pharmacokinetic data of tTF-NGR.

Primary Safety end-point

Maximum Tolerated Dose (MTD). MTD is the dose below the dose leading to reproducible episodes of Dose Limiting Toxicity (DLT) in at least 2/6 patients. DLT will be characterized by clinical, blood and serum monitoring at specified time points before and during study period.

Secondary Safety end-points

- 1. Occurrence and frequency of inhibition of tumor blood flow as measured by contrast-enhanced Magnetic Resonance Imaging (MRI).
- 2. Occurrence and frequency of tumor response defined as Complete Response (CR), Partial Response (PR), or Stabile Disease (SD) as defined by RECIST criteria.

Descriptive statistics will be used.

12. Patient evaluation and follow-up

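### Lymphoma patients are eligible, but response and progression are classified by RECIST, a solid-tumour standard, for every patient

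*Combined protocol and SAP*

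**What the plan says.** Section 6.1 admits patients with "histologically proven or cytologically confirmed solid malignant tumor or malignant lymphoma". The title and synopsis say the same. No cap, stratum or special rule for lymphoma is given.

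Response is judged in one way for all patients. Section 5 states: "Antitumor activity and response will be determined according to RECIST criteria". Section 15 repeats it: "Disease response criteria are according to the RECIST guidelines". The secondary endpoint in Section 11, also in the synopsis, is "Occurrence and frequency of tumor response defined as Complete Response (CR), Partial Response (PR), or Stabile Disease (SD) as defined by RECIST criteria", and its analysis is described by "Descriptive statistics will be used".

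The category is also used during the trial:
- Under Sections 3.5, 5 and 10, tumour response or progression stops a patient's dose escalation.
- Under Section 10, an escalation patient with response or progression is replaced. The next patient starts from the highest dose level that the previous one reached without DLT.
- Under Section 7.4, progression ends treatment. Response, or stable disease at 8 cycles, ends escalation and leads to continued treatment.

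On corticosteroids, Section 14.1 says that if infusional reactions occur, "patients will be premedicated with chlorpheniramine, paracetamol and corticosteroids to prevent such reactions". It adds that none occurred in the first patients treated. Section 8 foresees a first application without premedication. Section 6.2 lists as an exclusion "clinical application of any other drug with known antitumor activity", and Section 7.3 states: "Administration of any other anti-cancer medication including chemotherapy and biologic therapy and other IMPs is not permitted during study period". None of these sections says how corticosteroids are to be regarded in a lymphoma patient.

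**The concern.** That RECIST is a solid-tumour standard and that lymphoma has its own response classifications is general professional knowledge; the protocol states neither. On that footing, the plan does more than leave a detail open. It prescribes for an eligible group an instrument made for other diseases.

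Two things are at stake. The first is the reported response frequency. Section 11 counts stable disease as response, so a lymphoma patient placed on the wrong side of the line between stable and progressive disease changes the numerator directly. The second is the escalation path. Escalation runs one patient at a time, so a misread category can change when a patient stops escalating and when the next one takes over.

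There is a smaller issue as well. Corticosteroids have antitumour activity in lymphoma (again general knowledge, not in the protocol). A lymphoma patient premedicated after a reaction would receive such a drug on study while Sections 6.2 and 7.3 bar other antitumour treatment. A response first seen after that exposure would be hard to read.

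**Working it through.** **1. The passages side by side.** Eligibility covers two disease groups (title, synopsis, Section 6.1). The response rule covers one instrument (synopsis, Sections 5, 11 and 15). No section links the second group to another instrument, removes it from the response analysis or lists it apart. The mismatch therefore follows from the stated rules.

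**2. The plan's own figure.** Section 16.1 gives a minimum of 7 patients: 1 escalation patient with DLT, 1 verification patient who reproduces it, and 5 at the next lower level. 1 + 1 + 5 = 7, which reproduces.

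**3. Weight of one patient.** At n = 7, one lymphoma patient is 1/7 = 14.3% of the denominator. At an assumed n = 15 it is 1/15 = 6.7%. This is one patient's weight, not an estimate of bias.

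**4. How likely the criteria problem is to arise.** The lymphoma share s is not stated; assume 5% to 30%. The chance of at least one lymphoma patient among 7 is 1 − (1 − s)^7:
- s = 0.05: 1 − 0.95^7 = 0.302
- s = 0.10: 1 − 0.90^7 = 0.522
- s = 0.20: 1 − 0.80^7 = 0.790
- s = 0.30: 1 − 0.70^7 = 0.918

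**5. How likely the corticosteroid problem is to arise.** It needs a lymphoma patient who has also had an infusional reaction. The reaction rate r is not stated; assume 5% to 30%, independent of disease type. The chance of at least one such patient among 7 is 1 − (1 − s·r)^7:
- s = 0.05, r = 0.05: 1 − 0.9975^7 = 0.017
- s = 0.10, r = 0.10: 1 − 0.99^7 = 0.068
- s = 0.30, r = 0.30: 1 − 0.91^7 = 0.483

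At every assumed pair this is well below the figure in step 4. The criteria gap is the main issue and the corticosteroid point is secondary.

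**6. Precision.** The exact (Clopper-Pearson) 95% interval is 0% to 41% for 0 of 7 and 0.4% to 58% for 1 of 7. The response frequency is very imprecise under any classification.

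**7. Reach into the primary endpoint.** Section 9 defines DLT by CTCAE grade and causal relation to the drug. Sections 9 and 10 define the MTD by DLT counts. Neither uses a response category, so RECIST can affect the MTD only indirectly, through who is treated at which level and when.

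**The case against.** The strongest case against has four parts.

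First, Section 6.1 requires at least one marker lesion measurable in two dimensions, so lymphoma without a measurable lesion cannot enter. Section 5 adds a central reading of percentage change in marker lesions by the study radiologist. This narrows the mismatch but does not remove it, because the categories are still RECIST categories.

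Second, Section 10 lets the investigator call progression clinically before 2 cycles, so RECIST is not the only trigger, and a replacement resumes at the highest DLT-free level. This stands. No change to a DLT count or to the MTD has been shown.

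Third, the endpoint is secondary and descriptive, with no test, threshold or decision rule attached. This also stands and limits the consequence. That both disease groups would be reported in one frequency is inferred from the plan's silence.

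Fourth, Section 14.1 is a specific prophylaxis clause and can be read alongside a ban on anti-cancer treatment. A reader might see an outright contradiction with Sections 6.2 and 7.3, but the tension appears only once corticosteroid activity in lymphoma is brought in from outside. What remains is a need to clarify. It has some practical weight, since Section 17 lists receipt of non-permitted medication as a reason to exclude a patient.

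A reader might also infer that response data from lymphoma patients in general cannot be attributed to tTF-NGR. The documents do not support that. RECIST affects how a response is classified, not what caused it. Corticosteroids follow only after a reaction, so any confounding is confined to lymphoma patients who have reacted, and to their later infusions.

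**Conclusion.** The point holds for classification. An eligible disease group is assessed by a standard made for another, and the result enters a reported endpoint and the conduct of escalation. One lymphoma patient carries 14% of the response denominator at the minimum sample size. The chance of at least one among 7 is 30% to 92% for assumed lymphoma shares of 5% to 30%. The DLT and MTD definitions are untouched.

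The corticosteroid point holds only as a clarification. The chance of at least one affected patient among 7 is 1.7% to 48%, on assumed shares and reaction rates of 5% to 30% each. The protocol gives neither rate. Section 7.3 already accepts the principle involved: it removes irradiated lesions from response judgement because another treatment acted on them. Nothing comparable is said for lymphoma patients exposed to corticosteroids.

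The change is worth making because it is cheap and the rule as written does not suit the population. It is not a threat to the primary objective.

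**What to change.** - In the synopsis and Sections 5, 11 and 15, classify lymphoma patients by a named CT-based lymphoma response classification (Lugano, for example) and keep RECIST for solid tumours. State that these categories also apply where Sections 3.5, 7.4 and 10 refer to response, stable disease or progression.
- List responses separately for solid tumours and lymphomas.
- Record corticosteroid premedication by cycle, if the eCRF does not already capture it. Flag in the listing any lymphoma response first seen after such exposure. Flagging is enough; removal from the frequency is not needed.
- Reconcile Section 14.1 with Sections 6.2 and 7.3 for lymphoma patients. Which premedication rule applies is for the sponsor to decide.

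The cost is wording in four places and possibly one eCRF field, with no change to sample size. The study radiologist is already in the plan. The study calendar does not name the modality for tumour measurements, so the sponsor should confirm that the planned imaging supports a CT-based reading. The downside is two very small groups. If 7 patients split 5 and 2, the exact 95% interval for no responses is 0% to 52% in the group of 5 and 0% to 84% in the group of 2, against 0% to 41% for all 7. Individual listings will say more than percentages.
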